## Background

Chronic Plantar fasciitis (CPF) is a common cause of plantar heel pain that is a result of a degenerative process of the plantar fascia and its surrounding perifascial structures [1]. It is the most common cause of heel pain, affecting 10% of the U.S. population, and one of the most common foot and ankle problems [2]. One study showed that individuals with this disease scored significantly lower in general health-related quality of life in addition to foot specific quality of life (pain and function) [3]. In addition to a decreased quality of life, significant financial costs arise for these individuals: it is estimated that annual cost of treating this disease in the United States is 192-376 million dollars [4].

The plantar fascia, or plantar aponeurosis, originates on the posterior tuberosity of the calcaneus and inserts into the proximal phalanges of the toes. It acts like a cable, which tightens with flexion of the metatarsophalangeal joints, the "windlass" mechanism, thereby restoring the arch during mid-stance, stiffening the medial column of foot for pushoff and transferring the force of the gastrocnemius muscle contracture to the ground [5]. Although the exact etiology of CPF is unclear, the predominance of evidence indicates that it is the combination of age and overuse which lead to degenerative changes within the fascia that result in the symptoms associated with this disease [1]. The most common presentation for patients with plantar fasciitis include pain with the first few steps in the morning, pain at the beginning of the activity that resolves with continued activity, pain and stiffness with prolonged standing, and pain at the end of the day [6].

The diagnosis of CPF is made clinically based on history and physical exam [6]. Confirmation with diagnostic imaging may be necessary when the symptoms are atypical or are refractory to treatment. MRI is a useful diagnostic tool to evaluate for plantar fascia thickening and edema in and around the fascia, both of which are consistent with the diagnosis of CPF. In addition, many physicians use MRI to exclude other causes of plantar heel pain [7]. Ultrasound can also be used to quantify the thickness of the plantar fascia. Multiple studies have shown that patients with CPF have increased thickness of the fascia compared to asymptomatic individuals [8-12]. Mean thickness in these studies for subjects with CPF range from 4.8-6.5 mm as opposed to 2.3-4.0 mm for subjects without the disease [8-13]. One of the studies showed that the thickness was increased in medial, central and lateral bands of plantar fascia uniformly along with 68% of patients with CPF reporting central band tenderness as opposed to 26% having lateral band tenderness [12]. In addition to the evidence of inflammation [9], the presence of a hyperechoic lesion in the plantar fascia was noted in 68% [10] to 84% [8] of patients with

CPF. Diagnostic ultrasound has also been used to quantify the effectiveness of treatments such as extra-corporeal shock wave therapy, NSAIDs and Botox injections for subjects with CPF [11, 13].

More than twenty different treatments have been used for plantar fasciitis [14]. The combination of rest, ice, stretching and NSAIDs are used as initial management in most patients and have been shown to effectively treat symptoms in 90% of patients in less than 12 months [6]. However, 10% of patients fail conservative management and continue to have symptoms beyond 12 months (termed refractory plantar fasciitis or RPF) [1, 15, 16]. Surgery consisting of partial plantar fascia release or gastrocnemius recession is often considered in these patients. However, the outcomes of surgery are not uniformly positive with 50% of patients having residual symptoms. Moreover, evidence supporting surgical treatment of RPF is weak as there are no randomized controlled trials comparing its efficacy to other treatments. Thus, for many patients the risks of surgery such as arch instability, prolonged wound healing, and longer rehabilitation times simply outweigh the benefits [1]. ITU may be a non-invasive treatment that can be used as an adjunct to speed healing in patients with CPF and as an alternative to surgery in those with RPF.

### ***Intense Therapeutic Ultrasound (ITU)***

Various types of ultrasound have been used to treat soft tissue injuries since the 1930s [17]. Intense therapeutic ultrasound (ITU) is a recently developed ultrasound based therapy in which sound waves are concentrated to produce selective thermal coagulative change over a small area while leaving the remaining regions unaffected [18]. ITU has been used clinically for treating the facial skin for the past decade and it has recently received FDA approvals for non-surgical brow and submental tissue lifting. Over 1,000,000 patients worldwide have been treated using this technology. Clinical studies have shown that 85% of subjects receiving this treatment on facial skin tissue showed an improvement in facial lifting with no significant pain, erythema, inflammation or scarring [19, 20]. Histologically, it has been shown that ITU induces the production of dermal collagen with thickening of the dermis and straightening of the elastic fibers in the reticular dermis [18]. On-going research in our laboratory has shown that ITU can improve healing of damaged Achilles tendon in a rabbit model [21]. Preliminary results showed an increase in markers for wound healing (e.g. VEGFa, TNF  $\alpha$ , IL-1  $\beta$ , and TGF  $\beta$  1) and a decrease in markers for scar tissue formation (e.g. COL1a1, COL1a2, and COL2a1) in injured rabbit tendon treated with ITU compared to injured, untreated rabbit tendon. These results have led us to want to explore the possibility using ITU to treat patients with CPF.

Sept 2014 – present, ITU treatment for Plantar Fasciosis is currently being studied at the University of Arizona (University of Arizona - IRB approval #: 1404296558). To date we have completed 28 subjects with no adverse effects noted. Preliminary results were published August, 2015.

### ***Purpose of Study***

The purpose of this study is to assess the effectiveness of ITU in the treatment of CPF by assessing pain, function, and change in perifascial lesions treated with ITU in addition to standard of care. The primary outcome measures will be clinical grading for plantar fasciitis/osis grading and subject reported questionnaires where pain, function and level of activity will be compared before, during and at 24 weeks after the first of 2 treatments. In addition diagnostic ultrasound images will assess the change of any perifascial hypoechoic lesions. Finally, the safety and tolerability of ITU will be monitored through the course of the study. It is hypothesized that patients receiving ITU in addition to standard of care will have a more rapid resolution of their pain, faster return to activities, and a decrease in perifascial lesions.

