### ***Interventions***

Standard of care treatment will include massage 5 minutes daily as defined by PI and the use of an immobilization boot along with an orthotic insert for 2 to 4 weeks after the each treatment. The decision to continue or discontinue the boot will be made during the follow-up phone call 2 weeks after each treatment. The caller will discuss (Appendix 1-F) the subject's progress and come to a decision on continuing or stopping the use of the boot. When it is determined that a subject can stop using the boot, they will continue to use the orthotic insert in firm soled shoe that does not flex or bend – Tennis shoe, platform, wedge, Birkenstock or FitFlop™ sandal. At that point the subject can resume light activities: Walking on a flat, hard surface (no hiking trails), bicycling and light exercises. Subject will massage region twice a day for 2 ½ minutes per each time, total 5 minutes/day.

During Visit 2 (4 weeks after the first treatment), subjects will receive a second treatment if heel pain is not 90% resolved. The use of the boot and orthotic will resume as defined after the first treatment. If a week 4 visit is not possible we will allow a 2nd treatment at week 6, if such treatment is deemed necessary. If a 2nd treatment is moved to week 6, subsequent follow-up dates will be adjusted accordingly. ITU treatments will be performed using a GEN III system (Guided Therapy Systems, Mesa, AZ, Appendix 4). Trained study personnel will conduct the treatments. The treatment session will last 15 – 20 minutes. During this time the subjects will be required to lay prone on an exam table with their feet hanging over the end of the table. An average energy up to 5 joules / thermal zone will be administered to the plantar fascia in a linear pattern (Figure 1) with up to 360 thermal zones. Each thermal zone will be less than 1 mm^3 in volume, centred at 10 - 15 mm depth, and approximately 1-3 mm apart.

[figure not shown]

Figure 1: The treatment site located around the insertion of the plantar fascia onto the posterior process of the calcaneus

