#### Outcome measures

Subjects will complete subject reported outcome instruments, and will undergo a focused physical examination and diagnostic ultrasound at 0, 4, 8, 12 weeks. At 2, and 24 weeks a phone survey will be administered by the Clinical Coordinator using the same subject report outcome questionnaires. Adverse events, if any, and treatment tolerability will be recorded at each visit and 2-3 days after each treatment.

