#### Aim 1: Subject reported outcomes and structured physical exam

The principal aim of this study is to demonstrate the efficacy of treatment and time course of response to treatment and post treatment regimens using validated subject reported outcome measures assessing pain, function and level of activity and structured physical examination. Subjects will complete validated subject reported outcome questionnaires assessing pain, function and level of activity prior to initiating treatment and at 4, 8, 12, and 24 ( 24 week surveys will be completed by a phone interview) weeks after starting treatment. Subjects will also be contacted 2-3 days following each treatment to assess treatment tolerability and to document and address adverse effects (if any). They will also be contacted by phone 2 weeks after

treatment(s) to assess progress and determine if the boot can be discontinued.

**Pain** will be assessed using the of the foot function index pain subscale (FFI-P) and the subject reported outcome measures (SROM). These two instruments have been used to assess pain in previous studies of plantar fascia treatments. [22, 23]

**Function** will be assessed using two validated PRO instruments the PROMIS PF CAT and the FAAM. The PROMIS PFCAT is a subject relevant outcome measure that uses computer adaptive survey questions to assess the subject's pain and function in relation to daily activities [24]. The FAAM has been shown to be a reliable, responsive, and valid measure of physical function for individuals with a broad range of musculoskeletal disorders of the lower leg, foot, and ankle [25].

**Level of Activity** will be assessed using the activity subscale of FAAM. This subscale scores quantitatively the level of difficulty subjects face when they perform basic activities of daily living. It has shown to be an accurate and reliable predictor of the activity level while performing day-to-day activities [25]

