#### Statistical analysis

Data will be assessed for variance homogeneity and normality. FFI-P scores, PFCAT, FAAM scores before and after intervention will be compared using a paired t-test. Perifascial lesion volume is measured before and at each post treatment clinical visit using diagnostic ultrasound imaging, and paired t-tests will be utilized for comparison. For determination of statistical significance, a cutoff value of  $\alpha=0.05$  has been selected prior to start of data analysis.

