**Timeline**

Procedures	Visit 0	Visit 1	Visit 1 Follow-up Phone Interview Treatment Tolerability	Treatment 1 Follow-up Phone Call: Boot Decision	Visit 2	Visit 2 Follow-up Phone Interview Treatment Tolerability	Treatment 2 Follow-up Phone Call: Boot Decision	Visit 3	Visit 4	Phone Interview Subject's Progress Survey 2	Responsibility
	Baseline -14 - 0 Days	Week 0	Week 0 (+ 2 or 3 days)	Week 2	Week 4	Week 4 (+ 2 or 3 days)	Week 6	Week 8	Week 12	Week 24	
IC, eligibility paperwork, exam for inclusion criteria	X										PI/Clinical Coordinator (CC)
Ultrasound Imaging		X			X			X	X		GTS or PI
ITU Treatment		X			X (If required)						GTS or PI
TBD Clinical grading for Plantar Fasciitis severity	X	X			X			X	X		PI (cc documentation)
Subject Survey – Pain Scale and Ankle Mobility Scale		X			X			X	X	X Phone Interview	Subject (cc documentation)
Boot and Instructions		X		X			X If 2nd Treatment is Performed				PI (cc documentation)
Shoe, Insert and Instructions		X		X			X If 2nd Treatment is Performed				PI/CC
Follow-up call Treatment Tolerability			X			X If 2nd Treatment is Performed					PI/CC
Telephone Interview & Determine if Boot is continued (Week 2 and 6 only)				X			X If 2nd Treatment is Performed				PI/CC

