## Appendix 1-D: Foot function index pain subscale (0 – 10)

How severe is your heel pain?

---

1. At its worst?	No pain	Worst pain imaginable
------------------	---------	-----------------------

---

2. After you get up in the morning with the first few steps?	No pain	Worst pain imaginable
--	---------	-----------------------

---

3. At the end of the day?	No pain	Worst pain imaginable
---------------------------	---------	-----------------------

---

4. When you walk barefoot?	No pain	Worst pain imaginable
----------------------------	---------	-----------------------

---

5. When you stand barefoot?	No pain	Worst pain imaginable
-----------------------------	---------	-----------------------

---

6. When you walk wearing shoes?	No pain	Worst pain imaginable
---------------------------------	---------	-----------------------

---

7. When you stand wearing shoes?	No pain	Worst pain imaginable
----------------------------------	---------	-----------------------

---

8. When walking with orthotics?	No pain	Worst pain imaginable
---------------------------------	---------	-----------------------

---

9. When standing with orthotics?	No pain	Worst pain imaginable
----------------------------------	---------	-----------------------

---

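### A declared primary outcome, the clinical grading, is undefined and has no analysis, and no outcome or visit is decisive among several tested at 0.05

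*Protocol*

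**What the plan says.** **Primary outcomes.** The protocol's Purpose of Study says: "The primary outcome measures will be clinical grading for plantar fasciitis/osis grading and subject reported questionnaires". It continues that pain, function and activity "will be compared before, during and at 24 weeks after the first of 2 treatments".

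**The grading.** The Timeline row reads "TBD Clinical grading for Plantar Fasciitis severity". It is marked at Visits 0 and 1 (both before or at first treatment) and at Visits 2, 3 and 4, the last being week 12. The structured examination under Aim 1 lists findings to record but gives no grade or score.

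**Follow-up.** Clinic visits fall at weeks 0, 4, 8 and 12. The Outcome measures section adds: "At 2, and 24 weeks a phone survey will be administered by the Clinical Coordinator". Aim 1 lists the questionnaires at baseline and weeks 4, 8, 12 and 24. The SAP's last pain time point is week 26.

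**Analysis.** The protocol says "FFI-P scores, PFCAT, FAAM scores before and after intervention will be compared using a paired t-test", without naming the later visit, and adds paired t-tests of lesion volume, measured at each post-treatment clinic visit. The SAP applies t-tests between baseline and later follow-ups for self-reported and lesion-size measures. It also computes, at each time point, the share of subjects whose 0-10 pain score fell by at least 25%. Both documents set the significance level at 0.05, and neither mentions multiplicity or sidedness.

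**The concern.** A primary outcome should be defined, collected at a stated time and analysed by a stated method. The grading meets none of these fully: its scale is open, its baseline is one of two visits, and no test is assigned to it. Followed literally, the plan leaves one of its own primary outcomes unreported.

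The rest of the primary set does not fill the gap. Aim 1 sets out to demonstrate efficacy, yet an efficacy statement could rest on whichever questionnaire and visit reached 0.05. The reader of the results could not tell whether that result was the planned one, and the chance of a false positive somewhere in the set would exceed the nominal 5%.

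**Working it through.** The documents give no power calculation, sample-size derivation or familywise error rate, so there is no figure of theirs to reproduce. The check has two parts.

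**1. The grading, traced through the documents**

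- Purpose of Study: primary outcome.
- Timeline: scale undetermined; Visits 0 and 1 both pre-treatment; last mark at week 12; no mark at the week-24 phone interview.
- Structured physical examination: findings listed, no score.
- Statistical analysis: FFI-P, PFCAT, FAAM and lesion volume only.
- SAP: 0-10 pain, FFI, lesion volume and a lesion-pain correlation only.

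The pages between Appendix 1-F and Appendix 3 are not in the text available for review, so a grading form there cannot be ruled out. A form would not supply the missing analysis.

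**2. The number of tests and what it implies**

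The documents do not state the number of tests. The defensible readings are:

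- Protocol, one later visit: 3 questionnaires × 1 = 3.
- Protocol, each visit (weeks 4, 8, 12, 24): 3 × 4 = 12.
- The same plus lesion volume at weeks 4, 8 and 12: 12 + 3 = 15.
- SAP, outcomes it names: pain 4 + FFI 4 + lesion 3 = 11.

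Assume two-sided tests at 0.05, no true change in any outcome, and a common correlation ρ between test statistics. The documents give no correlations, so ρ is shown over a range. With c = 1.96, the chance of at least one false positive among m tests is

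1 − ∫ φ(z) [Φ((c − √ρ z)/√(1−ρ)) − Φ((−c − √ρ z)/√(1−ρ))]^m dz,

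which becomes 1 − 0.95^m when the tests are independent.

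| Reading | m | ρ = 0.9 | ρ = 0.7 | ρ = 0.5 | Independent |
|---|---|---|---|---|---|
| One test | 1 | 5.0% | 5.0% | 5.0% | 5.0% |
| 3 questionnaires, one visit | 3 | 8.4% | 10.9% | 12.5% | 14.3% |
| SAP named outcomes | 11 | 13.1% | 22.3% | 30.4% | 43.1% |
| 3 questionnaires, four visits | 12 | 13.5% | 23.2% | 31.9% | 46.0% |
| Plus lesion volume | 15 | 14.4% | 25.6% | 36.1% | 53.7% |

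A simulation of paired t-tests with n = 30 (the protocol's maximum) and 20,000 replicates agrees. For ρ = 0.9, 0.7 and 0.5 it gives 13.5%, 23.7% and 32.7% for 12 tests, and 15.0%, 26.1% and 36.7% for 15 tests.

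**The case against.** **The week-12 end may not be a fault.** A reader might infer that the plan fails to collect its primary grading at the primary time point. The text does not establish this. In Purpose of Study the 24-week clause can be read as applying only to the questionnaires, and a clinic-based grading that ends with the last clinic visit is then consistent. The gap exists only if the 24-week comparison is meant to include the grading.

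**The test count can be inflated.** Pooling both documents, testing the week-2 call and splitting the FAAM into two scores gives 28 tests, and 49% at ρ = 0.5. The support is weak. Aim 1 lists no week-2 questionnaire and the Timeline marks no subject survey then. Aim 1 does say activity "will be assessed using the activity subscale of FAAM", but Appendix 1-B prints a single 21-item list with one global percentage. Lesion volume is introduced after the primary sentence and has its own aim, so for the declared primaries the count may be as low as 3.

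**The SAP does have a target.** The 25% pain-reduction goal is its leading outcome. Aim 1 does not name the 0-10 scale among its pain instruments, but the Timeline schedules a pain-scale survey and Appendix 1-C prints such a scale. This narrows the criticism without removing it: the goal is not designated primary, is computed at every time point, and has no threshold at which the study succeeds.

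**The no-change premise is unrealistic.** Everyone receives boot, insert and massage, so some improvement is likely without any ITU effect. This stands. The percentages measure the looseness of the testing plan; they are not the probability of wrongly crediting ITU.

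**Conclusion.** The point holds on the text. One declared primary outcome is undefined, lacks a stated baseline and is analysed in neither document; this needs no assumption. Several other outcomes are tested at 0.05, with none decisive and no visit decisive.

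The size of the second part depends on assumed counts and correlations. Over ρ from 0.9 to 0.5 the chance of at least one false positive runs from 8.4% (three tests) to 36.1% (fifteen tests). Every multiple-test reading considered exceeds 5%.

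The documents do not support reading this as proof that week-24 grading data are missing, or as an estimate of the risk of a false ITU claim. Nor should a scoring bias be inferred from the FFI items such as "When walking with orthotics": neither document says how a blank is scored, and the point does not depend on it. The correction is worth making and is a matter of wording.

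**What to change.** 1. In Purpose of Study, Statistical analysis and the SAP, name one primary outcome at one time point, tested once at two-sided 0.05. If data have already been examined (the SAP is written in the past tense), label the choice post hoc.
2. FFI-P change from baseline by paired t-test is a candidate, because both documents analyse FFI pain. Either visit can be defended if the reason is stated. Week 12 is in clinic, avoids the 24/26 conflict and lies closer to the hypothesis of faster pain resolution. Week 24 is the visit that Purpose of Study names.
3. State whether the SAP's 25% responder goal is primary or secondary.
4. Define the grading's scale, baseline visit, time point and test, or remove it from the primary list with a stated reason.
5. Label all other outcomes and visits secondary or exploratory, reported with confidence intervals and no confirmatory claim.
6. Reconcile week 24 with the SAP's week 26. Say how the primary visit is dated when a second treatment moves and "subsequent follow-up dates will be adjusted accordingly". Reconcile the SAP's mention of control and treatment groups with the single-arm protocol before fixing the primary contrast.

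The cost is protocol and SAP wording only. Other outcomes can then no longer be presented as confirmatory, and a significant primary result would still not separate ITU from the boot, insert and massage.

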### ***Materials and Methods***

The **primary objective** of this study is to evaluate the efficacy of combining intense therapeutic ultrasound (ITU) with standard care, including post-treatment therapy, exercises and boot immobilization for the treatment

of chronic plantar fasciitis/osis. A **secondary objective is to** evaluate the tolerability and safety of intense therapeutic ultrasound in the treatment of plantar fasciitis.

These objectives will be accomplished through the following specific aims:

**Aim # 1:** Compare subject reported outcomes of pain, function and level of activity for all subjects before and after treatment. Follow the subjects for 24 weeks by clinic visits and phone surveys.

**Aim # 2:** Compare the changes in perifascial lesion volume for all subjects before and after treatment by diagnostic ultrasound imaging. Follow the subjects for 12 weeks by clinic visits.

**Aim # 3:** Evaluate the tolerability and safety of ITU for the treatment of the chronic plantar fasciitis.

